4.2 Study Outcome Measures

In order to capture all cases of UTI, and to enhance our ability to identify any symptom related to the urinary tract, we modeled when to have our follow up study visits and phone call after the FDA’s Guidance for Complicated and Uncomplicated Urinary Tract Infections [51,52]. We will have the:

- 1) Test-of-Cure Post-Treatment (TOC) Visit on Day 11 -14 (FDA recommendation: five - nine days after completing the study product); in order to evaluate the primary endpoint of symptomatic UTI. Secondary endpoints of asymptomatic bacteriuria, positive urine culture, and presentation of clinical symptoms that may be related to UTI will also be assessed.
- 2) Outcome Assessment Visit on Day 24 – 30 (14 – 20 days after completing the study product) in order to evaluate the secondary endpoints: recurrent infection (includes a relapse UTI or a reinfection) at any time after the TOC visit (Day 11-14); colonization with antimicrobial resistant *E. coli* and *K. pneumoniae* in the gastrointestinal tract; and
- 3) Follow-up call on Day 38 – 44 (FDA: 28-34 days after completing the study product). Safety follow-up during which subjects will be asked regarding presence or absence of UTI symptoms, if they sought medical care for possible recurrence of UTI, and if they experienced any inter-current illnesses.

4.2.1 Primary and Secondary Outcome Measures

The primary outcome measure is:

- Comparison of efficacy based on symptomatic UTI as assessed at the TOC visit (Day 11-14), between short-course and standard-course of antibiotics.

Since the primary objective of the study is to establish that short-course therapy is as effective as the standard therapy, the analysis of the primary endpoint will be based on a non-inferiority test. The primary analysis will be done on the intent to treat (ITT) population.

The secondary outcome measures are:

- Comparison of the number of subjects that have a recurrent infection (includes a relapse UTI or a reinfection) at any time after the TOC visit (Day 11-14), following short-course versus standard-course of antibiotics.
- Comparison of the number of subjects that become colonized with antimicrobial resistant *Escherichia coli* (*E. coli*) and *Klebsiella pneumoniae* (*K. pneumoniae*) in the gastrointestinal tract as assessed through Day 24-30, following short-course versus standard course of antibiotics.
- Comparison of the number of subjects with asymptomatic bacteriuria at the TOC visit, following short-course versus standard-course of antibiotics.

-
- Comparison of the number of subjects with clinical symptoms that may be related to a UTI prior to or at the TOC visit, following short-course versus standard-course of antibiotics.
 - Comparison of the number of subjects with positive urine cultures prior to or at the TOC visit, following short-course versus standard-course of antibiotics.

For a summary of individual subject study outcomes against the primary outcome measure see Table 2.

Sub-study Outcome Measures:

Seattle Children’s Hospital R21

- Presence of *E. coli*, presence of *K. pneumoniae*
- Sub-types of *E. coli* (0=phylogroups A or B1, 1=phylogroups B2 or D), sub-types of *K. pneumoniae*
- Presence of treatment-susceptible *E. coli*, presence of treatment-susceptible *K. pneumoniae*
- Presence of treatment-resistant *E. coli*, presence of treatment-resistant *K. pneumoniae*

Carbapenem resistant Enterobacteriaceae study

- Prevalence of colonization with carbapenem resistant *Enterobacteriaceae* in children after completion of the course of antibiotic therapy for UTI

Microbiome pilot study

- Comparison of the overall biodiversity of the gut microbial community, as measured by culture-independent marker gene sequencing at each follow-up visit following short-course and standard-course antibiotic exposure.
- Comparison of overall fraction of gut microbiome community represented by gammaproteobacteria measured by culture-independent marker gene sequencing at each follow-up visit following short-course and standard-course antibiotic exposure.
- Comparison of average ecological similarity between microbial communities within and between treatment groups at each follow-up following short-course and standard-course antibiotic exposure.

Spectrum of Stool Bacteria

- Description of the bacteria present on the aerobic stool cultures obtained at each the three study time points.

Table 2: SCOUT Study Possible Outcomes Day 6-44.

Outcome scenario	UTI Symptomology		Urine collection method	Urine culture result		Pyuria present		Composite Outcome/Follow-up	Repeat urine culture result/outcome	
	Symp	Asymp ¹		+	-	Yes	NO			
1	X		Clean Catch or Catheter	X		X		Treatment Failure		
2	X		Clean Catch or Catheter	X			X	No UTI		
3	X		Clean Catch or Catheter		X	X		Follow-up required. Contact subject in 24-48 hrs. Perform repeat urine culture if still symptomatic.	+	-
4	X		Clean Catch or Catheter		X		X	Follow-up required. Contact subject in 24-48 hrs - Perform repeat urine culture if still symptomatic.	+	-
5a		X	Clean Catch	X		X		No UTI (Asymptomatic Bacteriuria)		
5b		X	Bag	X		X		No UTI (Asymptomatic Bacteriuria)		
6a		X	Clean Catch	X			X	No UTI (Asymptomatic Bacteriuria)		
6b		X	Bag	X			X	No UTI (Asymptomatic Bacteriuria)		

7		X	Clean Catch or Bag		X	X		No UTI		
8		X	Clean Catch or Bag		X		X	No UTI		

¹ If a urine sample cannot be obtained from asymptomatic subjects at the TOC visit, another attempt will be made to obtain a sample at the Day 24-30 Outcome Assessment Visit. These subjects are evaluable for the primary endpoint measure (considered a success); however, they will not be evaluable for the asymptomatic bacteriuria or urine culture secondary endpoints.

[figure not shown]
Note: Urine collection in children that are toilet trained will be by clean catch. For infants and young children (prior to being toilet trained) the initial urine sample will be obtained by bag method (if asymptomatic), clean-catch if symptomatic (or catheterization if a sample cannot be obtained by clean-catch). Also see Section 9.2.3.1 for listing of urine collection by age group/symptomology.

5 STUDY DESIGN

The SCOUT Study is a multi-center, centrally randomized, double-blind, placebo-controlled non-inferiority clinical trial. Children will be stratified based on the presence of fever at initial presentation of UTI symptoms and by specific antibiotic therapy prescribed by the original treating clinical provider. Children who have demonstrated clinical improvement five days after starting the originally prescribed antibiotic (afebrile and asymptomatic) will be randomized to standard arm or the short-course arm. Subjects enrolled prior to completion of Day 5 of their originally prescribed antibiotic treatment, will be instructed to complete Day 5 dosing prior to initiating SCOUT study product on Day 6. Subjects enrolled Day 6 should not have started the Day 6 of their originally prescribed antibiotic treatment. The SCOUT study product will consist of trimethoprim-sulfamethoxazole sulfamethoxazole (TMP-SMX), cefixime, cephalexin and the corresponding placebos. If a child initially prescribed cefdinir is enrolled, they will be randomized to either five additional days of cefixime or the cefixime placebo.

About 746 subjects will be enrolled in order to reach 672 evaluable subjects, but the total number that will be ‘enrolled / consented’ may exceed 746 if the study has not enrolled 672 evaluable for the primary endpoint.

Figure 1: Randomization

5.1 Sub-studies

Seattle Children's Hospital R21

An R21-funded sub-study titled, “Differences in infecting and colonizing Enterobacteriaceae from short-course vs. standard therapy of pediatric UTI” is currently planned with collaborators at Seattle Children’s Hospital. This sub-study hypothesizes that both the antibiotic agent and the length of therapy will affect the patients’ indigenous flora and thus affect both the likelihood of recovering *E. coli* and/or *K. pneumoniae* from stool and the resistance phenotypes of the recovered isolates. The sub-study will utilize PCR- and sequence-based methods to characterize phylogenetic and resistance properties of the recovered isolates. The sub-study will also test the hypothesis that (1) *E. coli* and *K. pneumoniae* recovered from 2 or 3 stool cultures are more likely to be members of disease-associated subgroups within their respective species (*E. coli* phylogroups B2 and D, *K. pneumoniae* cluster Kpl); (2) treatment-susceptible strains recovered from cultures during treatment (culture #1 for 5-day arm; cultures #1 or #2, 10-day arm) are more likely to be members of disease-associated subgroups; (3A) treatment-resistant strains of either species are more likely than treatment susceptible strains to be recovered from cultures during treatment; and (3B) treatment susceptible strains of either species are more likely to be recovered from cultures during treatment in the AMC arm than in the TMP/SMX or CFX/CFD arms.

Carbapenem resistant enterobacteriaceae

For each enrolled research subject, the stool or perirectal swab collected at the Test of Cure visit will also be utilized to perform additional screening for the presence of carbapenem resistant enterobacteriaceae. The results of this additional screening will be used to determine the prevalence of colonization with carbapenem-resistant Enterobacteriaceae (overall and for specific pathogens) in ambulatory children after completion of treatment for UTI.

Microbiome pilot study

For each subject at CHOP who agrees to participate in the Microbiome pilot study, an additional perirectal swab and an anal swab will be collected. Subjects in diapers will also have a third additional stool swab collected if a soiled diaper can be obtained. The additional swabs will be collected at each visit and will be used to determine the composition of the subjects’ microbiome. Microbiome composition will be quantified using high-throughput DNA amplicon sequencing of 16S ribosomal RNA genes. The accuracy of microbiome analysis resulting from perirectal swabs will be tested via comparison with analysis performed on stool specimens. All samples will be shipped immediately or frozen overnight prior to shipment to collaborators at the University of Minnesota. Additionally, subjects agreeing to participate will be asked to complete a questionnaire providing data about feeding (breast milk, formula, timing of introduction of solid foods); most recent antibiotic prescriptions (name, dose, and duration); and number of antibiotic courses in life.

Spectrum of Stool Bacteria

For each enrolled research subject, the stool or perirectal swab collected at each visit will be used to identify any organisms present in the stool in addition to the organisms of interest for the SCOUT study, *E. coli* and *K. pneumoniae*. These organisms that grow from SCOUT stool cultures are already identified as a result of the processing taking place for the SCOUT study. In

this sub-study, the names of these other bacteria will be collected in a database to allow for a general description of the organisms that are present in children that are receiving antibiotic therapy for a urinary tract infection.

6 STUDY ENROLLMENT AND WITHDRAWAL

The two participating clinical trial centers, CHOP and PITT will enroll subjects over an approximately four and a half year enrollment period until 672 subjects have been enrolled that are evaluable for the primary outcome measure.

6.1 Subject Inclusion Criteria: Must Meet All

- 1) Age at randomization: at least two months (at least 36 weeks gestational age for subjects < two years of age) to 10 years of age (120 months)
- 2) Confirmed UTI diagnosis (see definition Section 3)
- 3) Documented Clinical Improvement at Randomization
 - a. Afebrile : No documented temperature equal or greater than 100.4 °F or 38°C (measured anywhere on the body) 24 hours prior to the enrollment visit

AND

- b. Asymptomatic: report NONE of the following symptoms:
 - Symptoms for all children (ages two months to 10 years):
 - fever (a documented temperature of at least 100.4 °F OR 38°C measured anywhere on the body)
 - dysuria
 - Additional symptoms for children > 2 years of age:
 - suprapubic, abdominal, or flank pain or tenderness OR
 - urinary urgency, frequency, or hesitancy (defined as an increase in these symptoms from pre-diagnosis conditions)
 - Additional symptoms for children ≥ 2 months to 2 years of age:
 - poor feeding OR
 - vomiting
- 4) Only children who have been prescribed one of the four antibiotics for which a placebo is available will be eligible to participate.
 - 1 TMP-SMX
 - 2 Cefixime
 - 3 Cefdinir
 - 4 Cephalexin

(Note a child that received a one-time dose of I.M. or I.V. medication (i.e. in ER or clinic) prior to starting on the one of the four oral medications is eligible for enrollment).

-
- 5) Parental/guardian permission (informed consent) and if appropriate, child assent (if \geq seven years of age).

6.2 Subject Exclusion Criteria: Meets at Least One

- 1) A urine culture proven infection with a second uropathogen $> 10,000$ CFU/mL collected via suprapubic aspiration or catheter or $> 50,000$ CFU/mL collected via clean void
- 2) A child hospitalized with a UTI that has the following: concomitant bacteremia associated with the UTI, urosepsis, or is in intensive care.
- 3) A child whose urine culture reveals an organism that is resistant to the initially prescribed antibiotic.
- 4) A child with a catheter-associated UTI.
- 5) A child with known anaphylactic allergies to the study products.
- 6) A child with phenylketonuria (PKU)
- 7) A child diagnosed with congenital anomalies of the genitourinary tract
- 8) UTI in children with known anatomic abnormalities of the genitourinary tract other than VUR, duplicated collection systems, and hydronephrosis.
- 9) A child that is not able to take oral medications
- 10) Previous surgery of the genitourinary tract (except circumcision in male children)
- 11) Presence of an immunocompromising condition (e.g., HIV, malignancy, solid-organ transplant recipients, use of chronic corticosteroids or other immunosuppressive agents).
- 12) Unlikely to complete follow-up (e.g. not available for the two follow-up study visits and the follow-up phone call)
- 13) A child with a known history of type I hypersensitivity of the study antibiotics to be prescribed
- 14) Enrollment in another antibiotic study less than 30 days prior to enrollment visit.
- 15) Previous enrollment of individuals in this study.
- 16) Planned enrollment during this study coincides with enrollment in another therapeutic drug study (excluding vaccine).
- 17) A child with a history of UTI within the past 30 days
- 18) A child with known Grade III-V VUR

19) A child taking antibiotic prophylaxis for any reason.

20) A child who has started Day 6 of the originally prescribed antibiotic treatment.

6.3 Recruitment Strategy

Children will be recruited from three different sources: primary care sites, general pediatrics inpatient units and the emergency departments from the following locations:

CHOP

- CHOP’s Inpatient Service;
- CHOP’s outpatient practice and urgent care network, which spans two states (Pennsylvania and New Jersey);
- The CHOP Emergency Department; and
- The General Pediatrics Inpatient Unit of CHOP.

PITT

- PITT’s Primary Care Centers;
- PITT’s Practice Based Research Network, PittNet;
- The PITT Emergency Department; and
- The Inpatient Service at PITT.

At both CHOP and PITT, SCOUT Study informational pamphlets will be prepared and distributed to all recruiting locations. These materials will explain the study, the criteria for inclusion and exclusion, and the study procedures and timeframe. These pamphlets can be used to familiarize primary care, ED and inpatient unit clinicians as well as subjects and families with the goals of the study. In addition, to further aid recruitment, a study webpage will be available for additional information for clinicians and subject families.

6.4 Treatment Assignment Procedures

6.4.1 Randomization Procedures

The SCOUT Study is a randomized, double-blind, placebo-controlled clinical trial.

After a potential subject has been determined to meet eligibility criteria, the subject will be given a random treatment assignment of study product to either short-course or standard-of-care therapy. Randomization will be done using fixed blocks of size four. Subjects will be stratified (within site) by febrile/non-febrile condition when originally diagnosed and antibiotic prescribed at initiation of therapy. That is, separate randomization sequences will be generated for each site for each of eight strata defined

by febrile/non-febrile condition and the four initially prescribed possible antibiotics. Treatment kits will be pre-packaged and randomized to active or placebo in a 1:1 ratio. Subjects initially prescribed cefdinir will be randomized to either cefixime or cefixime placebo.

The SCOUT Study will employ WesTrax™ an interactive voice response (IVR) system to randomize subjects. This system uses the telephone as a means to input data. Pre-recorded prompts are played listing the various options available to the user or requesting responses to particular questions. Data are entered using the telephone touch-tone keypad and are written to the underlying databases. The Study Nurse/Nurse Practitioner/Physician will randomize the subject based on the responses collected during the call into the system at the Enrollment Visit.

The system security is enforced through the recognition of unique User ID and PIN numbers assigned to each system user. Each PIN number is associated with a list of system privileges.

The Westat staff will train site personnel prior to study enrollment. In addition, at the time of site activation, each user at the activated site will receive an instruction packet. User instructions are project-specific and the packet will contain the necessary instructions for the user's appropriate system access level.

The WesTrax™ system will be available to all participating centers, 24 hours a day, seven days a week, with allowances for system maintenance operations, for the duration of study enrollment. If users have questions about the system, a WesTrax coordinator is on call 24 hours a day, seven days a week and can be reached by dialing the Help Center. All calls requiring action are recorded in a help desk database and metrics are readily available on calls for evaluation of additional training tool needs.

6.4.2 Masking Procedures

The study subjects and their families, investigators, and SCOUT Study team staff will remain blinded / masked to study treatment assignment (five more days of antibiotics therapy or five days of placebo) throughout the study. The subjects and their families, investigators, and SCOUT Study team staff will not be blinded to which one of the four antibiotics the subject was originally prescribed.

The study products and placebo will be prepared centrally, by the UPENN Investigational Pharmacy, for both CHOP and PITT. Only the Penn IDS Pharmacist will be aware of the study product bottle assignments. The staff at the medication storage areas at CHOP and PITT will be responsible for dispensing coded study products to preserve study blinding. For participants randomized to standard-of-care therapy, the pharmacy will provide the same medication prescribed to initially treat the UTI (NOTE: subjects initially prescribed cefdinir will be provided cefixime or cefixime placebo). The

Penn IDS pharmacy will prepare placebos that resemble the taste and consistency of the active antimicrobials. All study product kits will be packaged with an identical appearance.

The UPENN Investigational Pharmacy will maintain study product accountability records for both CHOP and PITT. The study product kits will be similarly labeled with a numerical code that masks site investigators, site staff, parent(s)/guardian(s) and children to the formulation. In addition, the UPENN Investigational Pharmacy will place a two-part label on each of the study product kits. One part of the label will be removed and placed on the subject’s case report form or the medication accountability log and the second part of the label will remain on the bottle. The Penn IDS pharmacist will be the only person to perform the unmasking if needed.

During the consenting process it will be explained to the parents of any potential enrollees that the study product (treatment or placebo) that will be provided after day five may or may not taste exactly the same as the originally prescribed medication, and look and smell slightly different because it will be provided to the study pharmacy from a manufacturer which may be different than the manufacturer who provide the medication for the first five days.

6.4.3 Reasons for Withdrawal

The SCOUT protocol has been developed to minimize the number of participants lost to follow-up and reduce barriers to participation. The schedule of contacts is designed to facilitate participant retention through regular contact in a short timeframe.

Participation in the SCOUT Study is voluntary. Subjects and their families can decide to discontinue participation at any time for any reason during the study by notifying study staff.

In addition, the Investigators may discontinue participation for any subject at their discretion: if in their professional opinion, the subject’s health, safety, and/or well-being is threatened by continued participation in the study or they may withdraw those subjects that do not comply with the study, or to protect the subject for safety reasons or for administrative reasons. Subjects may also be discontinued from the study at the Investigator’s discretion for lack of adherence to study treatment or visit schedules, AEs, loss to follow-up or a protocol violation.

Symptomatic subjects that develop a positive urine culture during the study period will not be considered withdrawn from the study, they will continue to be seen/contacted for any remaining study visits as part of safety follow-up. These subjects will be treated outside this protocol by a physician not associated with the SCOUT Study per current

standard of care or if they prefer the parent(s)/legal guardian(s) can choose to have their child treated by their PCP/pediatrician.

Subjects that develop a fever or worsening of symptoms after enrollment but prior to initiation of protocol treatment will be withdrawn from the study and considered entry failures. These subjects will be treated outside this protocol by a physician not associated with the SCOUT Study per current standard of care or if they prefer the parent(s)/legal guardian(s) can choose to have their child treated by their PCP/pediatrician.

It will be documented whether or not each subject completes the clinical study. If the Investigator becomes aware of any serious, related adverse events (AEs) after the subject completes or withdraws from the study, it will be recorded in the source documents and on the CRF.

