6.4.4 Handling of Withdrawals

All withdrawals regardless of reason (whether the SCOUT PI or the parent removed the child from the study), will be followed-up by a phone call one week after their withdrawal to determine their status and if any medical follow up care was sought (in which case an MCN form will be completed).

The Study Coordinator will collect data from the treating physician by completing the Medical Care Notification (MCN) Form.

Symptomatic subjects that develop a positive urine culture will not be considered withdrawn from the study. They will continue to be seen/contacted for any remaining study visits as part of safety follow-up. These subjects cannot be re-enrolled into this study. For symptomatic subjects with positive urine culture and pyuria during the Day 6 - 10 period the study product will be discontinued. Symptomatic subjects with positive urine culture will be treated outside this protocol by a physician not associated with the SCOUT Study per current standard of care or if they prefer the parent(s)/legal guardian(s) can choose to have their child treated by their PCP/pediatrician.

Subjects that withdraw or are withdrawn from the study prior to being evaluable for the primary outcome measure will be replaced.

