Safety Analysis: Safety in this study is related to efficacy. Safety will be evaluated by the collection and analysis of data on SAEs, clinical laboratory tests, pain assessments, and concomitant medications. The investigator is responsible for reporting all SAEs that are observed or reported up, regardless of their relationship to study product. Serious adverse events and abnormal laboratory (if available) results will be compared by treatment arm, with statistical tests for differences in proportion of subjects with serious adverse events between study arms.

Missing Data: Several procedures will be used to conduct data analysis when data for either outcomes or covariates are missing. The first step will be to assess the extent and pattern of missing data. If data are missing for only a few cases, then data analysis will be conducted only on study participants with complete data. However, when such a strategy would result in loss of data from a substantial proportion of participants or would lead to biased or inaccurate results, then some form of imputation will be performed. The form of imputation used will depend on the nature of the data that are missing.

Attrition and Loss to Follow-up: It is expected that loss to follow-up will be minimal in this study. Because the study is of short duration, we are hopeful that we will be able to follow virtually all subjects to study completion. However, some study participants may withdraw consent or may not return for the follow-up visits to determine the primary endpoint. Other participants may not have the endpoint determined due to problems with specimens or laboratory processing. We anticipate that these factors may reduce the sample size by as much as 10%. Thus the sample was increased by approximately 11% to offset this sample size reduction. Note that study participants who disrupt or discontinue study treatment will continue with follow-up and have the study endpoints assessed, and will be included in the ITT analysis.

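### The Protocol lets investigators remove a child from the study for not adhering to treatment, yet also says children who stop treatment stay in follow-up and in the ITT analysis

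*Protocol*

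**What the plan says.** **Removal from the study.** Protocol 6.4.3 gives investigators a discretionary power: "they may withdraw those subjects that do not comply with the study". It adds that subjects may be discontinued from the study "for lack of adherence to study treatment or visit schedules, AEs, loss to follow-up or a protocol violation".

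**After removal.** Protocol 6.4.4 says all withdrawals "will be followed-up by a phone call one week after their withdrawal", with a medical care form if care was sought. It also says: "Subjects that withdraw or are withdrawn from the study prior to being evaluable for the primary outcome measure will be replaced". SAP 2.4.2 repeats the replacement rule. Protocol 8.6 asks a child withdrawn before TOC to be assessed for symptoms and side effects, but states that no urine or stool is collected.

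**The opposite rule.** Protocol 12.4, in the paragraph on attrition, says that "study participants who disrupt or discontinue study treatment will continue with follow-up and have the study endpoints assessed", and that these children "will be included in the ITT analysis".

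**The SAP's accounting.** SAP 3.2 lists disrupting or discontinuing study treatment among the causes of the 10% sample loss for which enrolment is inflated.

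**The analysis set.** Protocol 12.4 and SAP 4.2.2 and 5.1 define the ITT population as children who took at least one dose and were either evaluated at TOC or failed before it.

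**The concern.** A child who stops or skips study product is non-adherent under 6.4.3 and may be taken out of the study. Under 12.4 the same child must stay in follow-up and be analysed. Nothing in 6.4.3 limits the discretion to cases that 12.4 leaves open, so the choice falls to the individual investigator.

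Adherence and adverse events are observed after randomisation, and they can differ between antibiotic and placebo. If removed children differ in failure risk from those who stay, and more so in one arm, the ITT set loses part of what randomisation gave it. In a non-inferiority trial the harmful direction is the loss of likely failures from the short-course arm, because that moves the result toward non-inferiority. Replacement restores the number of evaluable children but not the children who were randomised.

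**Working it through.** **1. The plan's own figures.** Inputs from SAP 3.2: 5% failure in both arms, 5-point margin, one-sided alpha 0.05, 90% power.

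- n per arm = (1.645 + 1.282)² × 2 × 0.05 × 0.95 / 0.05² = 325.4, so 326. This matches SAP 3.2.
- Inflation for 10% loss: 326 / 0.9 = 362.2 (SAP: 362 per arm). Protocol: 672 / 0.9 = 746.7 (stated as about 746).
- With the Protocol's 336 evaluable per arm, power is 90.8%.

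The sample size is not in dispute, and a consistent follow-up rule leaves it unchanged.

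**2. Following one child through the text.** The child takes a first dose on Day 6, stops on Day 8, and has no documented failure.

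| Step | Removed under Protocol 6.4.3 | Kept under Protocol 12.4 |
|---|---|---|
| Status | Out of the study | Off product, in follow-up |
| Next contact | Early termination visit and a call at one week | TOC, Day 11–14 |
| Urine | None at the early termination visit (8.6) | Collected from all subjects (8.3) |
| Can failure be shown there? | No: failure needs symptoms, pyuria and a positive culture (section 3) | Yes |
| ITT set | Outside, if neither evaluated at TOC nor failed before it | Inside |
| Replaced? | Yes (6.4.4) | No |

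Both columns are permitted. SAP 3.2 assumes something like the left column; Protocol 12.4 requires the right.

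**3. Who is exposed.** The primary analysis is affected only if all three conditions hold: treatment was disrupted or stopped, the investigator also ended study participation, and this happened before TOC without a documented failure. A child removed after TOC already has the primary endpoint. An adverse event or protocol violation without interrupted treatment does not conflict with 12.4.

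**4. Illustration only; the rates are assumptions.** Let true failure be 5% on standard and 10% on short course, exactly at the margin. Suppose a fraction w of short-course children is removed before TOC with failure risk q, none is removed from the standard arm, and replacement keeps 336 evaluable per arm.

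- Failure rate among those left: p = (0.10 − w·q) / (1 − w)
- SE = √[(0.05 × 0.95 + p(1 − p)) / 336]
- Chance of wrongly declaring non-inferiority = Φ[(0.05 − (p − 0.05)) / SE − 1.645]

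For w = 2% and q = 20%: p = (0.10 − 0.004) / 0.98 = 0.0980, SE = 0.0201, and the chance is Φ(0.10 − 1.645) = 6.1%.

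| w | q = 10% | q = 20% | q = 30% | q = 40% |
|---|---|---|---|---|
| 2% | 5.0% | 6.1% | 7.5% | 9.1% |
| 5% | 5.0% | 8.4% | 13.4% | 20.5% |

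When removed children carry the arm's average risk (q = 10%), nothing happens. The harm needs both selective risk and imbalance between arms. The table shows the direction and mechanism; it does not estimate what this trial would see.

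**The case against.** **The rules address different acts.** Section 12.4 is about stopping treatment; 6.4.3 is a power to end participation, which need not be used. A reader might infer that the two rules can never both hold. The documents do not support that: they collide only for treatment stoppers whom an investigator also removes. For those children the conflict stands, because a permission without limits sits beside a statement of what will happen.

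**Part of the separation already exists.** Section 8.2 has children with adverse reactions stop the product and does not mention leaving the study. Sections 6.4.3 and 6.4.4 expressly keep symptomatic, culture-positive children in. The per-protocol set is defined by an 80% dose threshold, which presupposes that poor adherers are retained for ITT. Section 16.6 handles deviations by reporting. All of this is correct and shows the intent, but it does not narrow the wording of 6.4.3.

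**The window is short and there are safeguards.** Product lasts five days. The diary and bottle are collected at TOC (7.5), so much non-adherence surfaces only once the child is evaluable. Staff and families are masked. The one-week call and medical care form could reveal a failure diagnosed elsewhere. SAP 4.2.6 foresees checks of missing endpoints, possible imputation and sensitivity analyses. These reduce the exposure. They do not replace a TOC assessment with urine.

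**A larger magnitude is tempting.** Take 373 per arm with 336 observed and 37 missing, 17 observed standard-arm failures, and 2 failures among the 37 missing standard-arm children. Observed short-course counts of 17, 20 or 22 give upper limits of 2.8%, 3.8% and 4.5%, all within the margin. They are overturned by 10, 7 or 5 failures among the 37 missing short-course children: each makes 27/373 against 19/373, with an upper limit of 5.04%. A reader might infer that this is the size of the present problem. It is not. It uses the whole 10% allowance, which Protocol 12.4 attributes to withdrawn consent, missed visits and specimen or laboratory problems, and it needs 14% to 27% failure among the missing (5/37 to 10/37) against a planned 5%.

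**A stricter remedy is tempting.** A reader might conclude that withdrawal should be confined to withdrawn consent or lost contact. That would override the safety discretion in 6.4.3, the removal of entry failures (6.4.3, 8.2) and the discontinuation of children whose organism proves resistant (8.1). The inconsistency gives no ground for that.

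**Conclusion.** The inconsistency is real and rests on the text alone. Protocol 6.4.3 permits removal from the study for conduct that Protocol 12.4 says will not end follow-up, and SAP 3.2 counts those children as lost. Through 8.6, the ITT definition and the replacement rule, a child removed before TOC without a documented failure disappears from the primary analysis and is substituted. The ITT comparison can thus be selected on behaviour after randomisation.

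The affected group is narrow and the effect on the result cannot be sized, because no withdrawal rate is given. The documents do not show that withdrawal would differ by arm, nor that the randomised comparison as a whole is lost. Correction is worthwhile because the gap bears on the primary analysis of a non-inferiority trial and the Protocol already states the right principle.

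**What to change.** Reconcile Protocol 6.4.3, 6.4.4, 8.6 and 12.4 with SAP 2.4.2 and 3.2 by separating two events: stopping study product, and leaving study follow-up.

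- **6.4.3:** state that non-adherence, or stopping product because of an adverse event or deviation, does not by itself end follow-up.
- **8.6:** state that children who have only stopped product are still asked to attend TOC with urine collection, and that the early termination visit is for those who leave follow-up.
- **6.4.4 and SAP 2.4.2:** state that a child is not replaced merely for stopping product.
- **12.4 and SAP 3.2:** use one account. Children who stop product are assessed and analysed as randomised, and are not part of the expected sample loss for that reason alone.
- Leave the existing provisions on safety discretion, entry failures, resistant organisms and withdrawn consent unchanged.

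The cost is an amendment to wording and a few more follow-up contacts. The TOC visit is already scheduled, and the evaluable sample size stays as planned.
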